5.4.2.2. BI 836826 Infusion Rate Response to Infusion-Related Reaction

If symptoms of an IRR occur while BI 836826 is administered, the following instructions for rate changes and interruptions of BI 836826 should be followed. Table 5-2 provides a tabular summary of procedures that may be employed to manage IRRs.

Table 5-2. BI 836826 Management of Infusion-Related Reactions

NCI CTCAE Grade of IRR	Action	Continuing BI 836826 ¹	
Grade 1	Reduce infusion rate to 50% of the rate at which symptoms occurred; infusion may be interrupted at investigator's discretion	After resolution of symptoms	Increase infusion rate to the rate at which the reaction occurred
Grade 2	Interrupt infusion; supportive treatment may be administered as indicated	After resolution of symptoms	Resume infusion at a slower rate than that at which the reaction occurred
Grade 3	Interrupt infusion; supportive treatment is typically indicated, glucocorticoids should be considered for management	After resolution of symptoms	Resume infusion at $\leq 50\%$ of the rate at which the reaction occurred x 30 minutes
Grade 4	Stop infusion	Do not re-expose	

1. Once subject is stable after reintroduction of initial infusion rate, proceed per Section 5.4.2, Dosage and Administration of BI 836826
 - In the case of an IRR of CTCAE Grade 1, the infusion rate of BI 836826 should be reduced to 50% of the previous rate, but may also be interrupted. Upon resolution of symptoms, the infusion may be resumed at an infusion rate not higher than the rate at which the IRR occurred, and escalated at the investigator's discretion within the limits described above.
 - In the case of an IRR of CTCAE Grade 2, the infusion of BI 836826 should be interrupted. Supportive treatment may be administered as indicated. Upon resolution of symptoms, the infusion may be resumed at 50% of the previous infusion rate and infusion rate escalated at the investigator's discretion within the limits described above.
 - In the case of an IRR of CTCAE Grades 3, the infusion with BI 836826 has to be stopped immediately. Supportive therapy is typically indicated, glucocorticoids should be considered for management. Once all symptoms have resolved, administration of BI 836826 may be resumed for at least 30 minutes at a rate which should not exceed 50% of the rate at which the reaction occurred. Re-increase of the infusion rate as tolerated by the subject is possible within the limits described above.
 - In the case of an IRR reaction of CTCAE Grade 4, the infusion has to be stopped immediately. Symptoms should be aggressively treated, glucocorticoids should be considered for management. Re-exposure after the event is not permitted.

5.4.2.3. Criteria for Administration of BI 836826 at 100% of the Assigned Dose (Day 22 and Following)

Prior to each administration of a 100% assigned dose of BI 836826, AEs and complete blood count (CBC) with differential will be assessed. To continue treatment with a further infusion of BI 836826, all of the following criteria must be met:

- Neutrophils ≥ 1000 / μ L (1.0×10^9 /L)
- Platelets $\geq 25,000$ / μ L (25×10^9 /L)
- Acceptable tolerability ([Table 5-3](#))

In case any 1 of these criteria is not fulfilled, blood counts and/or the AE should be regularly re-evaluated. See section [5.6](#) for information on dose modification in response to toxicity.

If an infusion cannot be administered within the protocol-specified procedure window (see [Appendix Table 1](#), Visit Window) the dose should be skipped. Doses may be made up if a minimum interval of 2 weeks is maintained between infusions. The last infusion of BI 836826 may be given no later than Week 48.

5.5. Dose-Limiting Toxicity

All AEs, including SAEs and deaths, will be carefully analyzed by the SRT. Dose-limiting toxicities will be those clinically relevant AEs which are unexpected in severity or frequency considering the mode of action and known toxicities of the individual agents, are not manifestations of underlying disease or background events typical of the study population, and are any of the following: debilitating, non-reversible, not manageable, or which lead to a fatal outcome, where evidence suggests that there was a reasonable possibility that the drug combination caused the AE.

The following drug-related hematologic adverse events will be considered DLT:

- Grade 4 neutropenia lasting more than 7 days
- Grade 4 febrile neutropenia, and Grade 3 febrile neutropenia not resolving within 48 hrs with appropriate treatment (antibiotics, antivirals, antifungals, growth factor support)
- Grade 4 thrombocytopenia lasting more than 7 days, or Grade 3-4 thrombocytopenia with clinically significant bleeding
- Grade 4 anemia
- Any Grade 5 hematologic AE

Non-hematologic, drug-related AEs of Grade 3 or higher will be considered DLTs except:

- Grade 3 ALT or AST elevation
- Grade 3 diarrhea that responds to therapy within 7 days
- Grade 3 rash that improves within 7 days following supportive therapy and discontinuation of idelalisib
- Grade 3 pneumonia or localized infection that responds to therapy within 7 days
- Any other Grade \geq 3 lab abnormalities that, in the opinion of the investigator, are attributable to the underlying disease process
- Infusion-related reaction, any grade

5.6. Safety Monitoring and Study Drug Interruption/Dose Modification/Discontinuation

Required and recommended actions for discontinuation or dose modification for both drugs, including the combination regimen, are provided in [Table 5-3](#). The requirements and recommendations are based on the drug and the CTCAE grade of specific toxicities, focusing on the types of events most commonly attributed to each of the study agents.

In cases of uncertainty, the study medical monitor should be contacted.

There is no limit on the length of time either idelalisib or BI 836826 may be held during the study (eg, to allow resolution of toxicity). If both idelalisib and BI 836826 are held during the same period, when appropriate both drugs should be restarted on the same day rather than dosing with idelalisib for 7 days prior to restarting BI 836826. During the combination therapy period (through Week 46), if either study drug is permanently discontinued, the other study drug should also be permanently discontinued. See Section [6.6.1](#) for recommended follow-up.

Table 5-3. Requirements and Recommendations for Discontinuation or Modification of Study Treatment in Response to Adverse Events

NCI CTCAE Grade ¹	Idelalisib	BI 836826
HEMATOLOGICAL ADVERSE EVENT		
Neutropenia		
Grade ≤ 2 neutropenia	Maintain current dose and schedule.	Maintain current dose level and schedule.
Grade 3 neutropenia	Required action: Blood counts must be monitored at least weekly until neutropenia Grade ≤ 2 .	Maintain current dose level and schedule. Consider G-CSF support. If febrile neutropenia not resolving within 48 hrs with appropriate treatment, decrease subsequent dose by 50% ² .
Grade 4 neutropenia (or occurrence of neutropenic fever or infection)	Required action: Interrupt idelalisib. Blood counts must be monitored at least weekly until neutropenia is \leq Grade 2. Recommended action: May resume idelalisib at lower dose level when neutropenia is Grade ≤ 3 ² . Neutropenia should be managed according to established clinical guidelines.	If Gr 4 neutropenia lasts >7 days, or febrile neutropenia not resolving within 48 hrs with appropriate treatment, decrease subsequent dose by 50% ³ Otherwise, maintain current dose level and schedule and consider G-CSF support.
Thrombocytopenia		
Grade ≤ 2 thrombocytopenia	Maintain current dose and schedule.	Maintain current dose level and schedule.
Grade 3 thrombocytopenia	Maintain current dose and schedule.	Maintain current dose level and schedule; unless associated with significant bleeding, in which case decrease subsequent dose by 50% ³
Grade 4 thrombocytopenia	Required action: During continuing single agent therapy period, withhold for bruising or bleeding until Grade ≤ 3 . Recommended action: During combination therapy period, maintain current dose level. If withheld during continuing therapy period, may resume at same or reduced dose level at investigator discretion ² .	If lasts > 7 days or associated with significant bleeding, decrease subsequent dose by 50% ³ .
Anemia		
Grade ≤ 3	Maintain current dose and schedule.	Maintain current dose level and schedule.
Grade 4	If all other possible etiologies of anemia have been ruled out, idelalisib may be withheld at investigator discretion.	Decrease subsequent dose by 50% ³ .

NCI CTCAE Grade ¹	Idelalisib	BI 836826
NON-HEMATOLOGICAL ADVERSE EVENT		
Rash		
Grade ≤ 2	Maintain current dose and schedule.	Maintain current dose level and schedule.
Grade ≥ 3	Required action: Withhold idelalisib until Grade ≤ 1. Recommended action: May resume at lower dose or discontinue idelalisib at investigator discretion ² .	Delay BI 836826 until Grade ≤ 1. Thereafter, may resume at full dose.
Stevens-Johnson Syndrome/Toxic Epidermal Necrolysis		
Any Grade	Required action: Discontinue idelalisib. Interrupt coadministered medications potentially associated with SJS or TEN. Institute treatment per institutional standards.	Discontinue BI 836826. Institute treatment per institutional standards.
Bowel Perforation		
Any Grade	Discontinue idelalisib.	Discontinue BI 836826.
Diarrhea or Colitis		
Any Grade (in addition see below for response to specific CTCAE grades)	Required action: See Section 5.7.2.1 for required assessments. Recommended action: Ensure good hydration status and provide anti-diarrheal; maintain current dose level. See Section 5.7.2.2 for recommended evaluations.	See below.
Grade ≤ 1	Required action: See Section 5.7.2.1 for required assessments. Recommended action: Provide anti-diarrheal (eg, loperamide) and maintain current idelalisib dose and schedule.	Maintain current dose level and schedule.
Grade 2 (unless clinical diagnosis is established from medical history and physical examination)	Required action: See Section 5.7.2.1 for required assessments and Section 6.1.8.9 for required testing. Recommended action: See Section 5.7.2.2 for recommended evaluations. Maintain current dose level.	Delay BI 836826 until Grade ≤ 1. Thereafter, may resume at full dose.
Grade ≥ 3 (or persistent Grade 2 diarrhea or colitis without clear etiology)	Required action: Withhold idelalisib. See Section 5.7.2.1 for required assessments and Section 6.1.8.9 for required testing. Consider anti-diarrheal (eg, loperamide) and/or addition of anti-inflammatory agent (eg, sulfasalazine, budesonide). Recommended action: See Section 5.7.2.2 for recommended evaluations. At Grade ≤ 1, may resume at lower dose level ² or discontinue study drug at investigator discretion.	If diarrhea Grade ≥ 3 recurs despite interruption of idelalisib, reduce BI 836826 to 50% ³ . BI 836826 may be increased to 100% upon resolution to Grade ≤ 1 at investigator discretion.

NCI CTCAE Grade ¹	Idelalisib	BI 836826
Hepatic Adverse Events (elevations in ALT, AST)		
Grade ≤1 (ALT/AST ≤ 3 × ULN; Bilirubin ≤ 1.5xULN)	Maintain current dose and schedule.	Maintain current dose level and schedule.
Grade 2 (ALT/AST ≤ 3-5 × ULN; Bilirubin > 1.5- ≤ 3xULN)	Maintain current dose and schedule. Recommended action: Monitor ALT, AST, ALP, and bilirubin at least 1x per week until all abnormalities are Grade ≤ 1.	Delay BI 836826 until Grade ≤ 1. Thereafter resume at full dose.
Grade 3 (ALT/AST > 5-20 × ULN; Bilirubin > 3-10xULN)	Recommended action: Withhold idelalisib. Monitor ALT, AST, alkaline phosphatase (ALP), and bilirubin at least 1x per week until all abnormalities are Grade ≤1. If bilirubin abnormality was Grade <3 resume idelalisib at same dose level. If bilirubin abnormality was Grade ≥3, resume at lower dose level ² .	Withhold BI 836826. Monitor ALT/AST at least 1x per week until Grade ≤ 1. Thereafter, may resume at full dose. If ALT/AST elevation Grade ≥ 3 recurs with BI 836826 at full dose and idelalisib at reduced dose, reduce BI 836826 to 50% ³ . Upon resolution of ALT/AST to Grade ≤1 BI 836826 may be re-escalated to 100% at investigator discretion.
Grade 4 (ALT/AST > 20 × ULN; Bilirubin > 10xULN)	Required action: Withhold idelalisib. Monitor ALT, AST, ALP, and bilirubin at least 1x per week until all abnormalities are Grade ≤1. If bilirubin abnormality was Grade 4, discontinue idelalisib. Recommended action: If bilirubin abnormality was Grade <4 resume idelalisib at lower dose level ² .	Withhold BI 836826. Monitor ALT, AST, ALP, and bilirubin at least 1x per week until all abnormalities are Grade ≤1. If bilirubin abnormality was Grade 4, discontinue BI 836826.
Pneumonitis (with new onset or worsening of baseline dyspnea, cough, or hypoxia without obvious infectious cause)		
Grade 1 (asymptomatic)	Required action: Withhold idelalisib until resolution to baseline. May resume at lower dose level or discontinue at investigator discretion.	Maintain current dose level and schedule.
Grade ≥ 2	Required action: Discontinue idelalisib permanently in subjects with any severity of symptomatic pneumonitis and institute therapy as clinically appropriate.	Discontinue BI 836826.
Pneumocystis jirovecii pneumonia (PJP)		
Any Grade	Required action: Discontinue idelalisib.	Discontinue BI 836826.
CMV Infection/Reactivation⁴		
Any Grade	Required action: Interrupt idelalisib upon unequivocal clinical or laboratory evidence of CMV infection. Treat according to established clinical guidelines. If the benefits of resuming idelalisib are judged to outweigh the risks, consider pre-emptive CMV therapy.	Discontinue BI 836826.
Hepatitis B Reactivation		
Any Grade	Required action: Discontinue idelalisib.	Discontinue BI 836826.

NCI CTCAE Grade ¹	Idelalisib	BI 836826
OTHER NONHEMATOLOGICAL ADVERSE EVENTS		
Grade ≤ 2	Maintain current dose level and schedule.	Maintain current dose level and schedule.
Grade ≥ 3	Withhold study drug until Grade ≤ 1. May resume study drug at initial or next lower dose ² or discontinue study drug at investigator discretion.	Withhold study drug until Grade ≤ 1. May resume study drug at initial or at 50% ³ or discontinue study drug at investigator discretion.

1. CTCAE, Version 4.03.
2. If assigned idelalisib dose level is 50 mg BID, dose reduction is not possible and idelalisib should be interrupted.
3. Dose reduction of BI 836826 by 50% may be performed twice. If still not tolerated, BI 836826 should be discontinued.
4. CMV should be diagnosed using clinical or laboratory criteria per established institutional standard

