Decrease in leukocytes, neutrophils, thrombocytes, and haemoglobin have frequently been reported in subjects. Drug-related neutropenia was reported in 41% (15/36) of the subjects, with a worst Common Terminology Criteria for Adverse Events (CTCAE) Grade 3 or 4 in 14/36 subjects (32%). Drug-related thrombocytopenia was reported in 31% (11/36), with a worst CTCAE Grade of 3 or 4 in 8 subjects (22%). Corresponding laboratory data showed that neutrophils and thrombocytes declined immediately after the infusion. Anemia was considered drug-related in 28% of the subjects and the highest Grade was CTCAE Grade 3. A drug-related increase of alanine aminotransferase (ALT) was reported in 4 subjects (11%), and an increase of aspartate aminotransferase (AST) was reported in 5 subjects (14%). ALT and AST elevations were Grade 1 and 2 in all subjects except for 1 subject with a Grade 3 ALT elevation. The corresponding laboratory data in these subjects showed short lasting, reversible elevations of AST and/or ALT without concomitant bilirubin elevation. Prior to the next administration of BI 836826, ALT and AST had returned spontaneously to normal or pre-treatment values.

Efficacy was observed at doses ≥ 9 mg. The Overall Response Rate (ORR) was 40% (12/30 subjects); all responses were partial responses. In addition, the decline in absolute lymphocyte count (ALC) was analyzed to assess effect of BI 836826 on CLL tumor load in 25 subjects treated at doses ≥ 9 mg, who had an elevated ALC at baseline and received at least 1 full dose of BI 836826 at the respective dose tier. A decline in ALC by 50% or more as compared to baseline was observed in 80% (20/25 of the subjects) and a reduction to $< 4 \times 10^9/L$ were observed in 56% (14/25) of the subjects.

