6.1.8.1. Chemistry and Hematology

Chemistry and hematology will be obtained a minimum of 3 times in the first week following the first 50% dose of BI 836826, and once after the first full dose of BI 836826, then a minimum of weekly x 6 weeks, then prior to each BI 836826 dose.

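### Table 5-3 says to maintain the BI 836826 schedule in Grade 3 and in short, uncomplicated Grade 4 neutropenia, which conflicts with Section 5.4.2.3 if neutrophils are still below 1000/µL on a full-dose day

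*Protocol*

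**What the plan says.** Table 5-3 in protocol Section 5.6 sets the response to each toxicity, with a separate column for each drug. In the BI 836826 column:

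- **Grade 3 neutropenia:** "Maintain current dose level and schedule. Consider G-CSF support". The dose is halved only if febrile neutropenia fails to resolve within 48 hours of appropriate treatment.
- **Grade 4 neutropenia:** the dose is halved if the event lasts more than 7 days or febrile neutropenia does not resolve. "Otherwise, maintain current dose level and schedule and consider G-CSF support".

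Section 5.4.2.3 governs each 100% dose, from Day 22 onward. AEs and a blood count are assessed beforehand, and "To continue treatment with a further infusion of BI 836826, all of the following criteria must be met": neutrophils at least 1000/µL, platelets at least 25,000/µL, and acceptable tolerability by reference to Table 5-3. If a criterion fails, the counts or the event are re-evaluated, and the reader is sent to Section 5.6 "for information on dose modification in response to toxicity". If the infusion cannot be given within the visit window, "the dose should be skipped. Doses may be made up if a minimum interval of 2 weeks is maintained between infusions".

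Neither neutropenia cell, nor the Section 5.6 text above the table, refers back to Section 5.4.2.3.

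**The concern.** After the first weeks of treatment, chemistry and hematology are drawn "then prior to each BI 836826 dose" (Section 6.1.8.1). An investigator holding a result below 1000/µL who looks up the neutropenia row finds an instruction to keep the schedule. Section 5.4.2.3 says the infusion must not go ahead. Its own pointer for a subject who fails a criterion leads to the table that says otherwise.

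At stake is a full antibody dose given to a neutropenic subject who is also on idelalisib, a drug for which Section 5.7.6 reports serious and fatal infections. Neutropenia is an expected toxicity here. Section 1.3.3 reports that neutrophils fell immediately after infusion in BI 836826 monotherapy, with drug-related neutropenia reaching "Grade 3 or 4 in 14/36 subjects (32"%).

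**Working it through.** **1. Where Grades 3 and 4 lie relative to the criterion.** The protocol does not print the CTCAE neutrophil limits. Section 5.7.5 requires at least weekly counts for Grade 3 neutropenia until it is Grade 2 or lower. Appendix 2, footnote 1, requires at least weekly counts for ANC 0.5 to < 1.0 × 10⁹/L. The matching rules imply that Grade 3 is ANC 0.5 to < 1.0 × 10⁹/L, and Grade 4 is lower still. The criterion is ≥ 1.0 × 10⁹/L (1000/µL). On that inference, ongoing Grade 3 or 4 neutropenia on a full-dose day always fails it.

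**2. The two rules side by side.**

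| Situation | Table 5-3 | Section 5.4.2.3 | Conflict |
|---|---|---|---|
| Day 8 (10 mg), Days 9 and 15 (50%) | keep schedule | does not apply | no |
| Neutropenia between infusions, recovered by the next | keep schedule | criterion met | no |
| Dose already reduced to 50% | keep schedule | written for 100% doses only | none as worded |
| Grade 3, or short uncomplicated Grade 4, still present on a 100%-dose day | keep schedule | hold; skip if outside the window | **yes** |

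**3. Which rule controls.** Section 5.4.2.3 makes Table 5-3 tolerability one of three conditions that must all hold. A permissive table entry can satisfy the third condition but cannot waive the first.

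**4. Reach.** From the Section 5.4.2 schedule:

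- 100% infusions: Weeks 4, 6, 8, 10, 12, 14, 16, 18 (8) plus Weeks 22, 26, 30, 34, 38, 42, 46 (7) = 15.
- Other infusions: Days 8, 9 and 15 = 3. Total 15 + 3 = 18, as planned.
- Share subject to the criterion: 15/18 = 83.3%.
- Appendix 2, footnote 4, says the subjects are past Week 16. At most Weeks 18, 22, 26, 30, 34, 38, 42 and 46 remain: 8 each, and 2 × 8 = 16 in total. This ceiling assumes every remaining dose is given at 100%.

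**5. Background rate.** 14/36 = 38.9%, exact (Clopper-Pearson) 95% CI 23.1% to 56.5%. The printed 32% does not match these counts, so the counts are used. They describe the worst grade at any time and any dose tier. They do not give the chance of a count below 1000/µL on an infusion day, which the documents do not report.

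**6. Can a held dose be made up?** The infusions at Weeks 18 to 42 are each followed by 4 weeks to the next. With the 2-week minimum interval, 4 − 2 = 2 weeks are available. Week 46 has 48 − 46 = 2 weeks before the Week 48 limit. So all 8 have up to 2 weeks.

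**The case against.** The strongest reply is that the protocol divides the work. No hematologic cell in the BI 836826 column contains a delay or a hold; those cells only keep or halve the dose. Delays and holds appear in the non-hematologic rows, such as rash, Grade 2 diarrhea and hepatic events. Section 5.4.2.3 sets numeric limits for neutrophils and platelets and leaves other toxicity to the table. The schedule in question is defined in Section 5.4.2, which contains 5.4.2.3 and its skip rule. The instruction to take a count before each full dose sits directly above the 1000/µL criterion, so a site would have to overlook the very limit the count is drawn to check. Section 5.6 also sends uncertain cases to the medical monitor.

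Much of this stands: it supports Section 5.4.2.3 as the controlling rule and makes an actual dosing error less likely. It does not remove the conflict. The neutropenia cells give an explicit timing instruction, in the same terms as the Grade 2 or lower row. The Grade 4 thrombocytopenia cell, by contrast, addresses only dose reduction and says nothing about schedule. A plain instruction to keep the schedule may also not strike a site as uncertain enough to call the monitor.

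A reader might infer that the table permits full dosing below 1000/µL, or that some 39% of subjects would be dosed while neutropenic. The documents support neither: the criteria are joint and mandatory, and no infusion-day rate is given. Nor do Section 5.7.5 and Appendix 2 state the Grade 3 range. One names a grade without a count and the other a count without a grade.

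**Conclusion.** The two cells are wrong as written for one situation: neutrophils still below 1000/µL on a 100%-dose day. Elsewhere the instruction to keep the schedule is not contradicted. Section 5.4.2.3 is the better-supported rule, so this is a minor safety inconsistency and does not mean that a safeguard is missing. It touches no estimate; the SAP plans safety listings only. Its practical reach is at most 8 infusions in each of 2 subjects, and no frequency of occurrence can be claimed.

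The conclusion rests on the inferred Grade 3 range and on reading Section 5.4.2.3 as limited to 100% doses, as it is worded. It is still worth correcting, because it concerns a dosing instruction for an expected toxicity and the correction costs almost nothing.

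**What to change.** In both BI 836826 cells (Grade 3, and the final clause of Grade 4), keep the existing instruction on dose level and schedule and add: *except that each 100% dose is given only when the Section 5.4.2.3 criteria are met (otherwise hold, skip or make up per 5.4.2.3)*. Keeping the reference to schedule preserves it for the 10 mg and 50% doses, where it is not contradicted. Leave the G-CSF and febrile neutropenia text unchanged.

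The cost is one phrase in two table cells, by clarification letter or amendment, with no new data or procedures. It holds no infusion that Section 5.4.2.3 does not already hold, and a held dose may still be made up within the 2 weeks shown above.

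### Table 5-3 delays BI 836826 for Grade 2 diarrhea or colitis but states no hold for a first Grade ≥3 episode

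*Protocol*

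**What the plan says.** Protocol Table 5-3 sets the response to adverse events separately for idelalisib and BI 836826. Three rows of the diarrhea or colitis block matter for BI 836826:

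- **Any Grade:** the BI 836826 cell only refers the reader to the rows below it.
- **Grade 2:** the row is labelled "Grade 2 (unless clinical diagnosis is established from medical history and physical examination"). BI 836826: "Delay BI 836826 until Grade ≤ 1. Thereafter, may resume at full dose". Idelalisib is maintained.
- **Grade ≥3:** the row is labelled "Grade ≥ 3 (or persistent Grade 2 diarrhea or colitis without clear etiology"). Withholding idelalisib is a required action. For BI 836826 the cell says "If diarrhea Grade ≥ 3 recurs despite interruption of idelalisib, reduce BI 836826 to 50" percent, then allows a return to 100% at Grade ≤1 at the investigator's discretion. It says nothing else.

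Section 5.4.2.3 lists conditions for every 100% dose: a neutrophil limit, a platelet limit, and "Acceptable tolerability ([Table 5-3").

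**The concern.** A dose-modification table should become stricter, or at least no looser, as the grade rises. Here a moderate event has a written delay for the antibody. A first severe event has none: the cell says neither to hold nor to maintain, and it speaks only to recurrence. A site that follows the table literally would find an instruction to delay the infusion at Grade 2 and none at Grade 3 or 4.

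The table is still in use. Section 5.4 lets the two enrolled subjects stay on both drugs at their current doses, and BI 836826 is scheduled through Week 46. What is at stake is dosing safety and consistency between sites. No estimate is affected: under SAP Sections 7.1.6, 7.6 and 7.7, safety data are listed only and dose-limiting toxicity is not evaluated.

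**Working it through.** The plan gives no figure to reproduce. The check is a comparison of texts and a count.

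**1. The diarrhea or colitis block**

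| Event | Idelalisib | BI 836826 |
|---|---|---|
| Grade ≤1 | maintain | maintain |
| Grade 2 | maintain | delay until Grade ≤1, then full dose allowed |
| Grade ≥3, first episode | withhold (required) | no action stated |
| Grade ≥3, recurring despite idelalisib interruption | withhold (required) | reduce to 50%; 100% allowed again at Grade ≤1 |

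**2. Comparable graded blocks in the BI 836826 column**

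- Rash, Grade ≥3: delayed until Grade ≤1, in the same words as the Grade 2 diarrhea cell.
- ALT/AST, Grade 3: "Withhold BI 836826. Monitor ALT/AST at least 1x per week until Grade ≤ 1". The recurrence rule comes only after that: if the elevation "recurs with BI 836826 at full dose and idelalisib at reduced dose, reduce BI 836826 to 50" percent. Grade 4 also opens with a withhold.
- Other nonhematological events, Grade ≥3: "Withhold study drug until Grade ≤ 1. May resume study drug at initial or at 50" percent, or discontinue.

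All three delay or withhold BI 836826 at Grade ≥3. The Grade 3 ALT/AST cell is closest in form. It has a recurrence rule, a 50% step and re-escalation, although its trigger differs. It has the opening hold that the diarrhea cell lacks.

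**3. Whether another section supplies the rule**

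- Section 5.4.2.3 sets its own limits only for neutrophils and platelets. Tolerability is referred back to Table 5-3.
- The row for other nonhematological events, by its heading, covers events not listed elsewhere in the table.
- Section 5.7.2 discusses idelalisib. Its only rule that reaches BI 836826 is to discontinue study treatment for bowel perforation.
- Section 5.6 allows holds of any length and directs uncertain cases to the medical monitor. That permits a hold but does not require one.

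**4. Who falls in the gap**

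The Grade 2 delay runs until Grade ≤1, and nothing in the Grade ≥3 cell lifts it. A subject who worsens from Grade 2, or whose Grade 2 event persists, is therefore generally already delayed. What remains is an event that starts at Grade ≥3 and is still at that grade when an infusion is due.

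**5. Reach**

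- Planned infusions: 4 (Days 8, 9, 15, 22) + 7 (Weeks 6, 8, 10, 12, 14, 16, 18) + 7 (Weeks 22, 26, 30, 34, 38, 42, 46) = 18, which agrees with the planned total.
- Appendix 2, footnote 4 says that subjects are past Week 16. Infusions that may remain are Weeks 18, 22, 26, 30, 34, 38, 42 and 46: at most 8 each, or 8 × 2 = 16.
- Section 5.7.2 gives a median onset of 7.1 months for Grade 3 or 4 diarrhea or colitis on idelalisib (range 0.5 to 29.8). 7.1 × 52/12 = 30.8 weeks, which lies inside Weeks 18 to 46. This is timing among patients who reported diarrhea or colitis, not an incidence.

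**The case against.** The strongest defence is that the cell is deliberate. Section 5.7.2 describes severe diarrhea as associated with idelalisib and resolving after its interruption, and the clinical summary of BI 836826 in Section 1.3.3 lists no diarrhea. Stopping idelalisib first, and touching the antibody only if the event recurs, is a coherent stepwise approach. The investigator's brochure, which might settle intent, is not among the documents. This explains the recurrence trigger. It does not explain the Grade 2 row, where BI 836826 is delayed while idelalisib continues.

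A second defence is that no sensible investigator would call active Grade ≥3 diarrhea acceptable tolerability. That is fair, and it keeps the severity low. But the criterion is defined by a table that is silent at this point.

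A third is that a reduction without a stated hold also appears for Grade 4 anemia. That is correct, but the anemia block is not inverted: lower grades are maintained and Grade 4 is reduced.

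A reader might also infer more than the documents support:

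- *That the protocol compels infusion during severe diarrhea.* It does not. Idelalisib must be withheld, and BI 836826 may be held.
- *That every other nonhematological block proves an omission.* Most of those blocks are outright discontinuations (for example SJS/TEN, bowel perforation, PJP, CMV, hepatitis B). They say little about graded holds.
- *That persistent Grade 2 without clear etiology is equally exposed because it shares the Grade ≥3 row.* It was Grade 2 first, so the delay would normally already apply.

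**Conclusion.** The inconsistency is real and of low severity. For BI 836826, Table 5-3 is weaker on paper at a first Grade ≥3 episode of diarrhea or colitis than at Grade 2, and no other section supplies the missing hold. The clear gap is direct-onset Grade ≥3 that is still active on an infusion day.

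Reach is at most two subjects and 16 infusions, assuming that neither subject had received the Week 18 infusion. Enrollment is closed, idelalisib is withheld in any case, and the documents report no such event.

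The effect per episode cannot be stated. A reader might divide the median resolution times in Section 5.7.2 (1 week to 1 month) by the 28-day infusion spacing and take the result as an upper bound on infusions affected. It is not a bound. Episodes can last longer than the median, time to resolution is not time at Grade ≥3, and some of those patients received corticosteroids. The incidence with this combination is not given either.

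The conclusion assumes that the extracted table cell is complete. Nothing in the row suggests missing text.

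**What to change.** Change the Grade ≥3 diarrhea or colitis cell in the BI 836826 column in two ways.

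1. Open it with an instruction to withhold BI 836826 until Grade ≤1, after which it may resume at full dose. This matches the Grade 2 diarrhea and Grade ≥3 rash cells and gives the Section 5.4.2.3 criterion a rule to point to.
2. Reword the recurrence trigger, for example: *if Grade ≥3 diarrhea or colitis recurs after BI 836826 is resumed, with idelalisib interrupted or at a reduced dose, reduce BI 836826 to 50%.* This is needed because Section 5.6 has both drugs restarted on the same day, when appropriate, if both were held. Recurrence during idelalisib interruption would then be hard to meet. Both conditions should be named, since footnote 2 of the table rules out a reduction for subjects assigned 50 mg BID and calls for interruption. Adding colitis matches the block heading.

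The cost is one table cell, with documented IRB/IEC approval before use under Section 9.2.1 unless the change is handled as reducing immediate risk. An infusion may be delayed or skipped. Section 5.4.2.3 lets it be made up if infusions are at least 2 weeks apart and the last is no later than Week 48, so a hold that covers Week 46 and runs past Week 48 could not be recovered. A BI 836826 delay of more than 4 weeks makes pre-medication mandatory for the first 8 weeks after restart (Section 5.4.2).
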